3.2 Sample Size

Eighteen healthy participants are planned for enrollment. It is estimated that a sample size of 14 completing subjects will provide at least 90% power at a 0.05 significance level to demonstrate an increase in 24-h urinary excretion of NDMA with ranitidine compared to placebo for a 1-sided log-transformed paired comparison. This assumes that geometric mean ratio between 24-h urinary NDMA with ranitidine and placebo is 2 and that the coefficient of variability is 100%. Enrolling 18 subjects allows for up to 20% dropouts.

Sample size calculations for the study are based on results from Zeng and Mitch (2016), which showed a 400-fold increase in NDMA for 150 mg ranitidine compared to placebo (47,600 ng versus 110 ng, respectively). The observed 24-h urinary excretion of NDMA with placebo for this and other studies ranged between 11-380 ng. It is not known if 24-h urinary excretion of NDMA with placebo is higher than what has been historically observed or if the fold-increase observed in Zeng and Mitch with ranitidine would be observed in a study controlling for meals with a randomized crossover design. The study sample size reflects assumptions that the overall fold-increase may be substantially lower but is still powered to detect an increase with assumptions as stated above.

4. Study Endpoints

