6.1 Handling of Missing and Incomplete Data

The following imputation of missing values will be done:

- PK measurements (urine or plasma) below the quantification limits will be considered equal to zero for all analyses.
- Missing PK data (e.g., skipped plasma sample collected or uncollected urine voids) will not be imputed.

7. General Statistical Considerations

All data will be presented in data listings. Data from subjects excluded from an analysis population will be presented in the data listings, but not included in the calculation of summary statistics.

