7.3 Pharmacokinetic Analyses

7.3.1 Urine Pharmacokinetics

The primary endpoint is a comparison of 24-h urinary NDMA excretion for ranitidine versus placebo when administered with either low nitrite/NDMA meals (comparison between treatments A and B, respectively) or high nitrite/NDMA meals (comparison between treatments C and D, respectively). No adjustment for multiplicity is planned as these comparisons are considered two separate studies for purposes of our overall design. As an exploratory analysis, 24-h urinary DMA for ranitidine versus placebo will likewise be compared between treatments A and B (low nitrite/NDMA meals) and treatments C and D (high nitrite/NDMA meals). 24-hr urinary excretion of ranitidine (exploratory) will be calculated for treatments A and C, though no

comparisons are planned. Finally, as an exploratory measure, the two placebo-treated treatments (treatment D versus B) will be compared to determine if meals comprised of foods traditionally identified as being higher in nitrites/NDMA result in a higher 24-hr urinary excretion of NDMA or DMA compared to meals identified as being lower in nitrites/NDMA.

The cumulative amount of NDMA (primary), DMA (exploratory), and ranitidine (exploratory) excreted in urine over 24-h for placebo and ranitidine administration will be calculated for each subject. All urine voids over a 24-h period will be collected. Each separate void will be weighed in a tarred container. The volume of the void will be determined assuming a specific gravity of 1.01. Concentration of each collected sample will be used to determine a cumulative amount excreted as follows:

$$Ae_{0-24, \text{compound}} = \sum_{\text{time}} \text{Urine}_{\text{weight, time}} * 1.01 * \text{Conc}_{\text{urine, time}}$$

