Cumulative amounts of DMA and ranitidine will be log-transformed. A mixed-effect analysis of variance (ANOVA) approach will be used for comparing arithmetic means (for NDMA) and geometric means (for DMA and ranitidine) looking at the effects of treatment, period, and sequence. For NDMA, testing will be one-sided at a 0.05 significance level, and a significant increase will be concluded if the lower bound of the one-sided 95% interval for the arithmetic mean difference excludes 0. For DMA and ranitidine, testing will be one-sided at a 0.05 significance level, and a significant increase will be concluded if the lower bound of the one-sided 95% interval for the geometric mean ratio excludes 1. The results will be transformed back to the original scale by exponentiation to provide treatment geometric means.

Normality assumption of the ANOVA will be verified using the Shapiro-Wilke test for normality and homogeneity of variances will be verified using Levene's test. If either assumption is not valid, a Wilcoxon signed-rank test will be used for the comparison rather than an ANOVA.

Individual and mean time course plots of NDMA, DMA, and ranitidine excreted over 24-hr will be evaluated for each treatment. All urine PK parameters will be summarized using descriptive statistics (number of subjects, mean, SD, coefficient of variation [CV], median, minimum, and maximum) for NDMA, DMA, and ranitidine. Individual time course plots will use actual sampling times. Treatment mean plots will use planned sampling times.

All calculations and the hypothesis testing will be done using R software.

Total fraction of the ranitidine dose excreted in urine ($Fe_{0-24, \text{ranitidine}}$) will be determined for Treatments A and C based on the cumulative amount of ranitidine excreted in urine over 24-h ($Ae_{0-24, \text{ranitidine}}$) divided by 300 mg. This will be calculated for each individual, summarized using descriptive statistics (number of subjects, mean, SD, CV, median, minimum, and maximum), and visualized graphically using box-and-whisker plots.

Renal clearance of ranitidine will be determined (only for Treatments A and C) by calculating the rate of excretion as the difference between the later and earlier compound level divided by the difference in times points (i.e., $[\text{amount}_{t_2} - \text{amount}_{t_1}] / [t_2 - t_1]$). The log-transform of the renal

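### SAP 3.2 still claims 90% power at 14 completers for a log-scale NDMA test that 7.3.1 no longer uses

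*SAP*

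**What the plan says.** SAP 3.2 estimates that "a sample size of 14 completing subjects will provide at least 90% power at a 0.05 significance level" to show an NDMA increase "for a 1-sided log-transformed paired comparison". The inputs are a geometric mean ratio of 2 and a CV of 100%. It adds: "Enrolling 18 subjects allows for up to 20% dropouts".

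SAP 7.3.1 log-transforms only DMA and ranitidine. For NDMA, an increase is concluded if the lower one-sided 95% bound "for the arithmetic mean difference excludes 0". The model is a mixed-effect ANOVA "looking at the effects of treatment, period, and sequence", checked by Shapiro-Wilk and Levene tests. "If either assumption is not valid, a Wilcoxon signed-rank test will be used for the comparison rather than an ANOVA". The low-meal (A v B) and high-meal (C v D) contrasts are unadjusted because "these comparisons are considered two separate studies for purposes of our overall design". SAP 6.1 adds: "PK measurements (urine or plasma) below the quantification limits will be considered equal to zero for all analyses".

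The version 2.0 change log lists edits to 7.3.1 and 7.3.2 only. Protocol 4.9.1 and 4.9.6.1 both work on the log scale, so the protocol agrees with itself.

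**The concern.** Two current SAP sections describe different primary NDMA tests, and the only power figure belongs to the one that is not used. The dropout allowance is derived from the same 14 completers, so it has the same basis.

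A reader cannot convert the figure. SAP 3.2 does not say whether the CV of 100% describes the paired ratio or a single measurement, and gives no within-subject correlation. Power on the arithmetic scale depends on both, and on how many 24-hour totals are zero.

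The risk lies in reading a non-significant result. The study asks whether a reported rise of about 400-fold is real, so a null result would be cited. If completers were close to 14, it would be read against a 90% figure computed for another test.

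**Working it through.** **1. Reproduce the stated figure.** Inputs from SAP 3.2: one-sided 0.05, ratio 2, CV 100%.

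- SD of the log difference = sqrt(ln(1 + 1²)) = sqrt(ln 2) = 0.8326.
- Noncentrality = sqrt(n) × ln 2 / 0.8326 = 0.8326 × sqrt(n), which is 3.115 at n = 14.
- Noncentral t with n − 1 df: 88.1% at 13, **90.4% at 14**, 95.9% at 18.

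So 14 is the smallest n reaching 90% on the log scale. Dropout: 14 / 0.80 = 17.5, rounded up to 18. Both figures reproduce.

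**2. What 3.2 leaves open.** If the CV is per measurement, the SD of the log difference is 0.8326 × sqrt(2(1 − ρ)). At ρ = 0 this is 1.177, the log-scale power at 14 is 67%, and 27 completers are needed. At ρ = 0.5 it is 0.8326, so the two readings coincide. I therefore use ρ = 0.5 as the central case; no passage states it.

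**3. Simulate the current rule.** Assumptions: lognormal pairs, ratio 2, log-difference SD 0.8326 (within-subject log SD 0.8326 / sqrt 2 = 0.5887), and Shapiro-Wilk and Levene checks each at 0.05 (the SAP gives no level). If either check fails, a one-sided signed-rank test is used; otherwise a paired t. No zeros, 100,000 trials:

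| Correlation | 0 | 0.3 | 0.5 | 0.7 | 0.8 | 0.9 |
|---|---|---|---|---|---|---|
| n = 14 | 87.0% | 84.9% | 82.9% | 80.6% | 78.5% | 75.9% |
| n = 18 | 93.9% | 92.6% | 91.5% | 89.7% | 88.7% | 86.5% |

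At ρ = 0.5, n = 17 gives 90.0%. On that basis 18 enrolled leaves room for one dropout (1/18, about 6%) before replacements.

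**4. Form of the ANOVA.** At ρ = 0.5, fitting A v B as its own crossover with period and sequence terms gives 82.2% at 14 and 91.0% at 18. A pooled four-treatment ANOVA gives 83.9% and 92.2%. Over correlations 0 to 0.9, neither moves the table by more than about 2 points.

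**5. CV per measurement instead.** At 14 the current rule gives 60 / 72 / 83 / 89 / 95% at ρ = 0 / 0.3 / 0.5 / 0.6 / 0.7. It passes 90% above about 0.6, but there the log-scale test would need only 12 (ρ = 0.6) or 9 (ρ = 0.7), so 3.2 would not have arrived at 14.

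**6. Zeros.** The change log reports subjects with whole periods below quantification but gives no share. For assumed shares of placebo totals at zero (ρ = 0.5, SD 0.8326, 40,000 trials):

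| Placebo totals at zero | 10% | 30% | 50% | 70% |
|---|---|---|---|---|
| Current rule, n = 14 | 84% | 84% | 82% | 74% |
| Log-scale test, zero pairs removed, n = 14 | 83% | 65% | 43% | 20% |
| Current rule, n = 18 | 92% | 92% | 90% | 85% |

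Over ρ from 0 to 0.8 with 10–70% zeros, the current rule spans 58–88% at 14 and 71–94% at 18.

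**7. Larger effects.** At 14, ρ = 0.5, no zeros: 92% at ratio 2.25, 96% at 2.5, 99% at 3.

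**The case against.** SAP 3.2 says nothing false: it names its test and inputs, and its arithmetic is right. The change log comes before it and announces the move to arithmetic means. Version 2.0 followed a blinded review of assay results, so the samples were already collected and no power figure could change N. On that view 3.2 is a record of how N was chosen, and one label would be enough.

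The size is also not derivable from the documents, since correlation, zero share, distribution and check levels are all assumed. The high-correlation rows are strained. Holding the log-difference SD at 0.8326, the total log variance is 0.3466 / (1 − ρ). The per-measurement CV is then 216% at ρ = 0.8 and 557% at ρ = 0.9. SAP 3.2 cites placebo excretion of 11 to 380 ng, about 35-fold; if those are individual values, such CVs look implausible.

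Much of this stands. The effect is small, the 0.8 and 0.9 rows deserve little weight, and 83% is conditional. But 3.2 is reissued in version 2.0 in the present tense, closes by saying the study remains powered under its assumptions, and carries no mark that the NDMA test changed. The change log does not mention it. Those points limit the size of the issue without removing the mismatch.

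**Conclusion.** The inconsistency holds between SAP 3.2 and SAP 6.1 and 7.3.1, all current text. The 90% at 14 and the 20% allowance belong to the log-scale test, and neither document shows that the current primary analysis has that power.

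With the SD that reproduces the sponsor's figure, and ratio 2, every correlation tried put the current rule below 90% at 14. It reaches 90% there only if the CV is per measurement and the correlation exceeds about 0.6. These figures rest on lognormal data and checks at 0.05; they are not bounds.

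The consequence is modest. With 18 completers (Protocol 4.5.2 allows up to 4 replacements) the central case is about 91–92%, and a ratio only slightly above 2 restores 90% at 14. Given the zeros that prompted version 2.0, the log-scale test would not have kept 90% either. The text should be corrected; the choice of analysis is not in question.

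**What to change.** In SAP 3.2:

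- Label the 90% at 14 completers and the 20% dropout allowance as the basis of the log-scale design, and say that they do not carry over to the version 2.0 NDMA analysis.
- State whether the CV of 100% is for the paired ratio or per measurement, and the correlation assumed.
- Give simulated power for the current rule at 14 and 18 completers as a range over correlation and share of zero totals, with the assumptions printed beside it (at correlation 0.5 with no zeros, about 83% and 91%).
- State the significance level of the Shapiro-Wilk and Levene checks used in that simulation.

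Enrolment and the analysis itself stay as they are. The cost is a short text edit and a simulation that runs in under a minute. The stated power at 14 becomes less favourable in the central case.

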4.1 Primary Endpoints

The primary endpoint of this study is 24-h urinary NDMA excretion.

4.2 Exploratory Endpoints

The exploratory endpoints of this study are:

1. AUC from time 0 extrapolated to infinity (AUC_{0-inf}) of plasma ranitidine, NDMA and DMA
2. Cumulative ranitidine and DMA amount excreted in urine over 24 h after ranitidine administration

5. Analysis Populations

The PK population will include all subjects who receive study drug and have at least one on-treatment sample. The safety population will include all subjects who receive at least 1 dose of any of the study drugs. The analysis population will include all subjects in the PK population with sufficient data to calculate PK parameters from at least two study periods of the same meal

type (i.e., low nitrite/NDMA or high nitrite/NDMA). Treatment in all analysis populations will be assigned based upon the treatment which the subjects actually received.

6. Data Screening and Acceptance

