**Study Design:**

This is a randomized, placebo-controlled, single-dose, 4-period crossover study with 18 healthy subjects with the following design:

Day -2	Day -1	Day 1	Day 2	Day 3	Day 4	Day 5	Day 6	Day 7	Day 8
Check-in	Washout	Period 1	Washout	Period 2	Washout	Period 3	Washout	Period 4	Checkout

The following 4 treatments will be administered over the 4 study periods. Each subject will be randomized to 1 of 4 treatment sequences (i.e., ABCD, ABDC, BACD, or BADC). FDA will prepare the randomization schedule. The treatments consist of oral administration of either a single dose of ranitidine (300 mg) or placebo administered at time 0 hr. All subjects will be provided low nitrite/NDMA meals for the first two periods of the study and high nitrite/NDMA meals for the last two periods of the study. This ordering of meals will allow purchasing a single lot of perishable items for different meals and to simplify meal preparation and serving at the study site.

Treatment Code	Treatment
A	Ranitidine + low nitrite/NDMA meal
B	Placebo + low nitrite/NDMA meal
C	Ranitidine + high nitrite/NDMA meal

D	Placebo + high nitrite/NDMA meal
---	----------------------------------

Subjects will report to the study site for screening from Days -28 to -3 and then will return to the site on Day -2 for baseline assessments. Subjects will receive three standardized meals per day starting on Day -1. Subjects will be served meals from a pre-specified menu for check-in and for all washout and treatment days. Subjects will be instructed to finish all their meals within 25 minutes with no leftovers. Subjects will only consume foods served to them at planned meal and snack times.

Two different full day menus of low nitrite/NDMA and high nitrite/NDMA meals have been developed. Additional details regarding the meals will be specified in the Meal Preparation Plan. Meals will be identical for treatments A and B (low nitrite/NDMA meal) of the study and a separate set of identical low nitrite/NDMA meals will be served on the washout days prior to treatment. Likewise, meals will be identical for treatments C and D (high nitrite/NDMA meal) and a separate set of identical high nitrite/NDMA meals will be served on the washout days prior to treatment. The last meal on Day -1, Day 2, Day 4, and Day 6 should be administered at approximately 6 PM to permit at least 12-hour fasting prior to dosing. Subjects will be provided with distilled water to drink throughout the study.

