#### 3.2. Exploratory Endpoints

The exploratory endpoints of this study are:

1. AUC0-inf of plasma ranitidine, NDMA and DMA
2. Cumulative ranitidine and DMA amount excreted in urine over 24 h after ranitidine administration

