2.0	General (Rationale)	NDMA analyses will be based on arithmetic means instead of geometric means. Blinded review of the bioanalytical data revealed that a large number of urine and plasma samples for NDMA were below the lower limit of quantification (LLOQ). For multiple subjects, all samples from 1 or more study periods were below the LLOQ. As zero values cannot be log-transformed for geometric mean analyses, these periods would have been removed from analysis. Furthermore, as analyses are paired, these subjects would have been removed from analyses. Utilizing arithmetic mean will allow data from all subjects and all periods to be used in the planned analysis. Ranitidine and DMA analyses will remain the same (i.e. utilizing geometric means).
	7.3.1	Analysis of urine concentrations Analysis of NDMA urine 24-hr excretion will be performed using arithmetic means instead of geometric means.
	7.3.2	Plasma pharmacokinetics Descriptive statistics for plasma PK parameters of NDMA will be calculated using arithmetic means.

1. Introduction

This document outlines the proposed statistical methods for data analysis of data collected from Protocol ‘SCR-010 Clinical study to investigate the urinary excretion of N-nitrosodimethylamine (NDMA) after ranitidine administration’.

2. Objectives

The following analysis plan provides the framework for the summarization of the data from this study. The analysis plan may change due to unforeseen circumstances but will be finalized prior to database lock. Any changes made after the database lock will be documented and justified in the clinical study report.

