7.3.2 Plasma Pharmacokinetics

The following PK parameters will be determined for NDMA, DMA, and ranitidine (only Treatments A and C) for each subject based on all available concentration-time points:

- **AUC from time 0 to the sampling time corresponding to the last quantifiable concentration (C_{last}) (AUC_{0-t})**

AUC_{0-t} will be calculated according to the linear trapezoidal rule from 0 h to the last quantifiable concentration after drug administration.

- **AUC from time 0 extrapolated to infinity (AUC_{0-inf})**

AUC_{0-t} will be extrapolated to infinity from the AUC from time 0 to the sampling time corresponding to the last quantifiable concentration plus the last quantifiable concentration divided by K_{el} , as follows:

$$AUC_{0-inf} = AUC_{0-t} + C_{last}/K_{el}$$

- **Maximum concentration (observed peak drug concentration) (C_{max})**

C_{max} will be read directly from the observed concentrations.

- **Time at which C_{max} occurs (T_{max})**

T_{max} will be read directly from the observed concentrations as the blood sampling time corresponding to C_{max} . The earlier time will be reported in cases where the same C_{max} value is observed for a subject at multiple timepoints

- **Terminal half-life ($t_{1/2}$)**

The terminal half-life will then be calculated using the elimination rate constant as:

$$t_{1/2} = \ln(2)/K_{el}$$

- **K_{el}**

The terminal elimination rate constant, which will be determined from the terminal slope of the log-concentration curve using linear regression

The PK parameters will be analyzed using noncompartmental methods based on actual sampling times. Serum concentrations below the limits of quantification will be set to zero for the purpose of this analysis (see Section 6). AUC_{0-inf} , $t_{1/2}$, and K_{el} for each analyte and subject will only be

included if the subject has 3 or more concentration values on the terminal portion of the pharmacokinetic curve and with an adjusted coefficient of determination (R^2) greater than 0.80.

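### AUC0-inf is not well defined for plasma DMA if a background or later meal input is present; a fixed 0–24 h area should be the tested endpoint

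*SAP*

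**What the plan says.** Protocol 3.2 lists "AUC 0-inf of plasma ranitidine, NDMA and DMA" as an exploratory endpoint, and SAP 4.2 repeats it: "AUC from time 0 extrapolated to infinity (AUC_{0-inf}) of plasma ranitidine, NDMA and DMA".

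SAP 7.3.2 sets out the derivation: "The following PK parameters will be determined for NDMA, DMA, and ranitidine (only Treatments A and C) for each subject". The restriction to A and C attaches to ranitidine, so DMA parameters are also derived in placebo periods B and D. Kel is the terminal slope of log concentration, and AUC0-inf is AUC0-t plus Clast/Kel. AUC0-inf, Kel and half-life are only "included if the subject has 3 or more concentration values on the terminal portion of the pharmacokinetic curve and with an adjusted coefficient" of determination above 0.80. The section does not say how the terminal points are chosen. It sets no limit on the extrapolated share, no pre-dose correction, and no rule for a pair in which one period fails. SAP 6.1 does not impute missing PK data.

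AUC0-inf and Cmax are then compared A versus B and C versus D, by paired t-test or Wilcoxon signed-rank test. AUC0-t is derived and summarised but not compared.

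On meals, the Protocol Synopsis says: "Subjects will receive three standardized meals per day starting on Day -1". On dosing days the first meal is given with the dose (SAP 3.1).

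**The concern.** AUC0-inf is meaningful when a single input at time 0 is followed by decay to zero. Ranitidine meets that description. DMA may not. In periods B and D no drug is given, so Kel has no dosed elimination to measure. If DMA returns to a non-zero background, the true area to infinity is unbounded and Clast/Kel estimates nothing. If a later meal adds DMA, the terminal slope follows that meal.

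Three places imply that DMA is expected without ranitidine and may respond to food. SAP 2.2 makes the effect of meal type on plasma DMA an objective. SAP 7.3.1 compares urinary DMA between the two placebo treatments, D and B. The version 2.0 change log moves NDMA off the log scale because many values were below the quantification limit, but says: "Ranitidine and DMA analyses will remain the same (i.e. utilizing geometric means".

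At stake is the only plasma comparison of total DMA exposure between ranitidine and placebo. It could lose pairs to the fit rule, or rest largely on extrapolated area.

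**Working it through.** **Plan's own figure.** No sample size is given for plasma DMA. The 18 used below is planned enrolment (SAP 3.2). That figure reproduces: with the SD of the log difference = √ln(1 + 1²) = 0.833 and a ratio of 2, 14 pairs give power 0.904 one-sided at 0.05. Then 14/(1 − 0.20) = 17.5, rounded up to 18.

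**Inputs from the documents.** Thirteen plasma samples at 0, 0.5, 1, 1.5, 2, 3, 4, 5, 6, 9, 11, 14 and 24 h (SAP 3.1); at least 3 terminal points and adjusted R-squared above 0.80 (SAP 7.3.2).

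**What the rule means with three points.** Adjusted R² = 1 − (1 − R²)(n − 1)/(n − 2). With n = 3 this is 1 − 2(1 − R²), so above 0.80 requires R² above 0.90.

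**Flat background, closed form.** For three points with independent log-normal noise and no true slope:

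P(R² > 0.90 and slope < 0) = ½[1 − (2/π) arcsin √0.9] = 0.102.

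A pair needs both periods: 18 × 0.102² = 0.19 pairs.

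**Other shapes, by simulation.** These inputs are assumptions, because the documents give no plasma DMA level, no DMA content of meals and no later meal times on dosing days:
- background 1, with meals at 0, 4.5 and 10 h;
- each meal adds a first-order peak (absorption rate 1.5/h, elimination rate 0.35/h) with amplitude 0.3, 1 or 3 times background;
- a peak of amplitude 0.5 added in the ranitidine period;
- within-profile noise of 5, 10 or 20%;
- terminal points either the last three or the best fit after Cmax;
- 3,000 pairs per setting.

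| Assumed DMA profile | Pairs kept, of 18 | Median extrapolated share in placebo periods that pass |
|---|---|---|
| Flat background | 0.2–0.3 | 58–88% |
| Small meal peaks (0.3×) | 1–5 | 46–62% |
| Moderate peaks (1×) | 4–13 | 28–32% |
| Large peaks (3×) | 7–18 | 12–13% |

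Ranges run over noise level and choice of terminal points. As a control, a single-dose profile with no background passed in every simulated case, with about 0.3% extrapolated.

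**Precision.** Among the few surviving flat-background pairs, the SD of the log ratio was about 0.6–1.0 for AUC0-inf and about 0.02–0.12 for the area over the sampled 24 h.

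**Testing with few pairs.** Five pairs give a smallest possible two-sided signed-rank p-value of 2 × (1/2)⁵ = 0.0625. SAP 7.3.2 does not state whether the plasma tests are one- or two-sided.

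**The case against.** The strongest reply is that the harm depends on facts that the documents do not contain. The meals are described by nitrite and NDMA content, and only nitrite, NDMA and nitrate may be assayed; DMA is not listed. Whether meals alter DMA is posed as a question. The 6 PM last meal is specified for Days -1, 2, 4 and 6, not for dosing days. The change log does not say why DMA stays on the log scale, so quantifiable DMA is an inference. All of this stands.

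A reader might infer that the comparison will lose most pairs or be mostly extrapolation. The documents do not support that as a general statement. With large meal peaks, the last three points and 5–10% noise, 17–18 of 18 pairs survive with about 12% extrapolated. A reader might also infer that surviving pairs are selected on treatment response. That requires ranitidine to change the plasma DMA profile materially, which the trial is there to find out.

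Other measures also give protection. The R-squared rule is meant to withhold unreliable values, AUC0-t is summarised, and Cmax and 24-hour urinary DMA are compared A–B and C–D. If DMA is quantifiable at 24 h, AUC0-t is essentially the area over 0–24 h.

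The gap left is that this observed area is not tested while the extrapolated one is. Nor does passing the fit rule rescue the parameter: with large peaks the slope passes because it tracks the last meal, so the reported Kel and half-life would not describe the study dose.

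**Conclusion.** The point holds in conditional form. AUC0-inf, Kel and half-life are not well defined for plasma DMA if there is a background level or later meal input. The plan applies them to placebo periods without a limit on extrapolation or a rule for lost pairs.

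The size is a range: about 0.2 to 18 of 18 pairs kept, and about 12% to 88% of the area extrapolated, depending on the assumed meal peaks, noise and choice of terminal points. The closed-form 10.2% pass rate is exact for a flat profile and three points, but it is the unfavourable end of the range.

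Severity is minor and confidence moderate. One analyte of one exploratory endpoint is affected; the primary urinary NDMA analysis and its sample size are not. This is a cheap improvement.

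**What to change.** In SAP 4.2 and 7.3.2 and Protocol 3.2, name AUC0-24 as the plasma DMA exposure endpoint, by linear trapezoid over the planned 0–24 h samples. Do not subtract the pre-dose value, because the paired placebo period carries the background. Run the A–B and C–D comparisons on it. Do not derive AUC0-inf, Kel or half-life for DMA; keep them for ranitidine. Align the parameter lists in the Protocol Synopsis, 4.7.1.3 and 4.9.6.2.

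The cost is wording only. The samples are already planned, and with complete sampling all 18 pairs are kept because no terminal fit is needed. The downside is that the exploratory endpoint label changes for one analyte.
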